7. STUDY SCHEDULE

7.1 GENERAL EVALUATION INTAKE

Treatment-seeking individuals will undergo the CNRA general evaluation protocol (HSC-MS-05-0322). Those who complete this protocol will be eligible for Study 64, based on random allocation to study method.

7.2 STUDY SPECIFIC

7.2.1 ENROLLMENT/RANDOMIZATION

An urn randomization procedure will be used to assign subjects to one of the four treatment groups. This procedure will balance groups on important pretreatment characteristics that may influence measures of cognitive performance and/or treatment outcome. The variables will include (1) severity of cocaine dependence, based on days using cocaine in past 30; (2) baseline (trait) impulsivity score, based on the Barratt Impulsiveness Scale (BIS). The BIS was chosen as a variable for the urn randomization because it has norms for high and low impulsivity in cocaine users based on previous studies and has been predictive of treatment retention.

Treatment assignment will be concealed to all clinical and research staff, including the investigators. Only the study pharmacist who dispenses the study medication will be unblinded to participants' assigned condition.

7.2.2 BEHAVIORAL LAB ASSESSMENT

The following behavioral/cognitive laboratory measures will be administered by a trained research assistant at designated time points. To ensure validity and compliance, eligibility for lab testing will require estimated premorbid IQ levels > 80 (Shipley-2) and the absence of acute cocaine intoxication on the day of testing (based on examination of DSM-IV symptoms and urine drug screen results). One hour prior to testing all cigarette-smokers will be prompted to smoke one cigarette in a designated outside area. This 60-minute window has been used in previously funded work at the CRNA to control for the potentially confounding effects of either nicotine withdrawal or acute nicotine stimulation.

The Iowa Gambling Task (IGT) is a computerized version of the original Iowa Gambling Task. Subjects are asked to choose between four decks of cards that result in theoretical monetary rewards at different rates. Each deck (labeled A, B, C, and D) contains 60 cards. Subjects must make 100 choices over the testing session. We will use versions of the IGT developed for repeated administration, provided to us through collaboration with [name], who developed the task. The primary dependent variable to be used in the statistical analyses will be the net score for the IGT, calculated as the total number of cards selected from the advantageous minus the disadvantageous decks [(C+D)-(A+B)] across five blocks of 20 cards each.

The Risky Decision-Making Task was developed specifically for the assessment of acute drug effects and repeated measurement over time. Like the IGT, it is a computer-based task that provides subjects with different options over 112 repeated trials, defined as non-risky (net gain

.01, no loss) and risky (gain/loss of 0.25, 0.50, 0.75, or 1.00 with gain/loss probability = 0.50).

Like the IGT, the non-risky option is more adaptive over many trials. Subjects start each test session with \$6.00. End-of-session earnings can range from approximately +\$14.00 to -\$2.00 depending on choice patterns. Unlike the IGT, earnings are real money that count toward subject payment at the end of the experimental day. The primary dependent variable will be the number of choices on the risky response option.

The Continuous Performance Test (CPT). The version of the CPT that will be used for this study is the Immediate Memory Task (IMT). The IMT is a paradigm based on the continuous performance task, originally developed as a measure of attentional capacity and the ability to withhold a prepotent response. Subjects are required to respond selectively to a series of stimuli (e.g., numbers) presented briefly for 500 ms with a 500 ms ITI. Go/No-Go paradigms have also shown sensitivity to acute stimulant effects. Increases in false alarm rates are interpreted as failures in response inhibition. Five-digit numbers are presented on a computer screen every 500 ms sec. Subjects are instructed to respond when the first number of a set is repeated. A 'hit' response is scored when a subject correctly responds. Distracter stimuli consist of five-digit numbers that are completely different from the first, and numbers in which four of the five digits match the original, with the non-matching number occurring randomly across the five digit places. A response to a distracter is scored as a 'false alarm' and operationally defined as a failure in response inhibition. The primary dependent variable will be the percent of false alarms.

The Progressive Ratio (motivation) Task. We operationally define motivation as a change in responding that is functionally related to a change in its consequences. Specifically, in the procedure described below, we interpret the allocation of behavior to a response option with increasing response requirement and corresponding increases in reward (money) value as an index of motivation. The procedure presents subjects with two mutually exclusive response options: a progressive-ratio (PR) reinforcement schedule and a fixed-time (FT) reinforcement schedule. Monetary rewards are periodically represented by a counter located near the top of the on-screen display. The PR schedule is programmed on one option (work). The initial response requirement on the work option is 10 responses, and produces a reinforcer of \$0.01. After each reinforcer, the response requirement is increased by ten percent of the previous value and the reinforcer amount is increased by \$0.01. Thus, each subsequent reinforcer is worth more than the previous one, but requires more work to obtain it. These parameters effectively serve to produce earnings that maintain subjects' attention, maintain PR responding throughout at least half of the session, and avoid exceptionally large ratio sizes.

Also available during the session is a second option (non-work), which is available at any time. Once the non-work option is selected, no responses are required to earn monetary rewards – money simply accumulates by being added to the counter after fixed time-intervals have elapsed. Importantly, once the non-work option has been selected, it is in effect for the remainder of the session, and this change is not reversible. The non-work option amount and time value are yoked to the performance on the work option: the reward amount is exactly 66% of that earned on the last completed PR (work), and the time interval for each reward delivery is either the time that was required to complete the last PR or 120 sec, whichever is larger.

Thus, the non-work option always delivers a smaller amount of money than the next scheduled reward on the work option. The two options are indicated by response boxes located on the right and left sides of a computer screen, and the terms work and not-work are not used.

The PR and FT schedules can be thought of as work and non-work options because (a) the work option requires increasing behavioral output and the non-work option requires no behavioral output, and (b) the contingencies are arranged such that it is advantageous to remain on the work option, even when the PR requirement reaches very high values near the end of the session. The primary dependent variables of interest will be the largest PR completed on the work option.

The Cocaine Stroop. The task is administered on a desktop computer, and assesses attentional biases to cocaine-related (drug-related) and appetitive (non-drug related) stimuli vs. neutral stimuli. Drug-related, non-drug related, and neutral words are presented in separate blocks of 30 trials each. Block order is counterbalanced over participants with a short interval of a few seconds between blocks. *Stimulus Materials:* There are cocaine-related words (e.g., COCAINE, CRACK, ROCKS, HIT); neutral words consisting of outdoor features (BRIDGE, AVENUE, SIDEWALK) and indoor, household, features (e.g., ROOM, FLOOR, CABINET); and appetitive non-drug related words selected from items that our cocaine-dependent participants reported acquiring with the money they received (from CM) in previous pilot work (e.g., VACATION, FOOD, JEWELRY). Categories are matched on length and frequency of use. Participants are instructed that words written in different colors (blue, green, or red) are presented on the screen, one after the other, and that their task is to indicate as quickly and as accurately as possible which color the word is written in, by pressing one of three colored buttons on a keyboard. Participants are instructed to ignore the meaning of the word itself and just to respond to the color. On each trial, a word is presented in capital letters and remains on the screen until the participant presses a button. If the participant makes a wrong response there is a tone. If the participant makes no response within three seconds the word is removed (and there is a tone). Within each block, the order of words is randomly determined by the program for each participant under the constraint that the same color or word does not appear on two consecutive trials. The primary data analyses are focused on reaction times (RT) to make a response to each word. RTs less than 100 ms are eliminated, as are RTs on trials on which participants made an error. The cocaine Stroop effect (attentional bias) is the difference in RTs on cocaine vs. neutral words, and the difference in RTs on cocaine vs. non-drug related appetitive words. The cocaine Stroop effects are (normally distributed) difference scores reflecting the difference in reaction times across the separate stimulus types.

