1. ABSTRACT/STUDY DIAGRAM

Most cocaine dependent patients suffer from deficits in cognitive function that, if left untreated, predict poor outcome.

Purpose: The present study investigates a pharmacotherapeutic intervention designed to improve cocaine treatment success by combining medications that act simultaneously on dopamine, the brain system that is critically associated with chronic cocaine use and cognitive functions. **Procedures:** Treatment with levodopa/carbidopa plus ropinirole (tested at two doses) will be compared to levodopa/carbidopa alone, and placebo. Measurement of performance on behavioral/cognitive measures of decision-making, behavioral inhibition, reward motivation, and attentional bias will be conducted at treatment entry and at repeated time points during the 10-week treatment. It is hypothesized that treatment with levodopa/carbidopa + ropinirole will produce superior outcomes in terms of reduced cocaine use and increased treatment retention and that these effects will occur indirectly via improved performance on observed cognitive mechanisms. **Course of Study:** Eligible cocaine dependent patients will be randomized equally to one of four medication conditions. Outpatient treatment will last 10 weeks and consist of thrice-weekly clinic visits. The behavioral therapy platform for this trial will consist of weekly cognitive behavioral therapy (CBT). The primary outcome measure will be weekly mean proportion of cocaine non-use days. Secondary endpoints will include abstinence rates during the last 2 weeks of treatment, time in study, and medication compliance. **Enrollment:** This project requires a final intent-to-treat sample size of 200 subjects. To obtain this sample, we expect to conduct phone screens on ~ 640 individuals, of whom 320 (50%) will qualify, enroll, and start intake. Of the 320 who start intake, we expect that 200 (~60%) will complete intake and be randomized into the ITT sample. Based on these projections and recruitment rates achieved during our previous levodopa studies, 40 months will be allotted to complete study enrollment (~ 5 new subjects/month).

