Cognitive-enhancing DA Medications for Cocaine Dependence

NCT01393457

Version Date: 09/02/2011

STATISTICAL ANALYSIS PLAN (SAP)

Data will be entered by research assistants into an existing, relational database (i.e. Microsoft Access). Data integrity will be maintained by restricting allowable input values on standardized Access entry forms. Double entry of a random subset of 10% of the observations will be used to identify problematic data entry issues. Preliminary data analyses evaluating group differences on demographic and baseline variables will use contingency tables with chi-square testing, ANOVA's, and examination of correlations between baseline variables and specified outcomes. Baseline or demographic variables, on which group differences are detected and which are correlated with outcomes, meet the definition of confounders and will result in two sets of analyses: one in which the relevant variable is included as a covariate and one in which it is not. This will permit determination of the degree to which any group differences might confound conclusions regarding treatment.

Broadly, the data analytic strategy will use generalized linear modeling and mixed effects models. Longitudinal analyses will be conducted using generalized linear mixed modeling (Proc GLIMMIX; SAS 9.2) for both continuous and discrete outcomes. Count, dichotomous and time to event data will be evaluated using Poisson (Proc GENMOD; SAS 9.2), logistic (Proc GENMOD; SAS 9.2), and proportional hazards regression (Proc PHREG; SAS 9.2) respectively. Distributional assumptions will be evaluated via inspection of residual plots and, where possible, by formal statistical tests. Violation of assumptions will be addressed, depending upon statistical technique, through the use of transformations, robust estimators, scaling coefficients, and stratification. Sample size approximations are obtained through empirical data simulation using SAS v.9.2.

PRIMARY HYPOTHESIS TESTING: To evaluate the efficacy of combination levodopa/carbidopa-ropinirole therapy in treatment of cocaine dependence. H1. The combination of levodopa/carbidopa and ropinirole will reduce cocaine use and increase treatment retention. H2. There will be a dose-response relationship such that

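### The CPT's primary variable is the false-alarm percentage with no stated role for hits, so a general drop in responding could be read as better response inhibition

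*Protocol*

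**What the plan says.** Protocol 7.2.2 introduces the task as one "originally developed as a measure of attentional capacity and the ability to withhold a prepotent response", so it names two constructs, attention and inhibition. It defines two scores. For targets, "A 'hit' response is scored when a subject correctly responds". For distracters, "A response to a distracter is scored as a 'false alarm' and operationally defined as a failure in response inhibition". The direction of reading is explicit: "Increases in false alarm rates are interpreted as failures in response inhibition". The outcome for analysis is then fixed in one sentence: "The primary dependent variable will be the percent of false alarms".

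The protocol does not name a hit or omission rate, a discrimination or bias index, or a minimum hit rate for a valid session as part of the CPT analysis. It also does not say what the percentage is a percentage of.

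The SAP does not mention the CPT. Its hypothesis H1 concerns drug use and retention: "The combination of levodopa/carbidopa and ropinirole will reduce cocaine use and increase treatment retention". The cognitive tasks matter because the Protocol abstract proposes that "these effects will occur indirectly via improved performance on observed cognitive mechanisms".

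**The concern.** A false-alarm rate on its own mixes two things: how well a person tells targets from distracters, and how ready that person is to respond at all. Someone who is drowsy, disengaged or too slow for the stimulus rate will respond less to everything. False alarms then fall, and the plan's operational definition scores the fall as better inhibition. Only the hits show the difference, because they fall as well.

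The four arms receive different dopaminergic treatment, so a between-arm difference in general responsiveness is conceivable. If one occurred, it could be reported as a drug effect on inhibition and then carried into the claim that better cognition explains reduced cocaine use. The hypothesised pathway could appear supported by a change that was not inhibition.

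**Working it through.** **Reproducing the plan's figure.** There is none. The documents give no CPT rates, SD, effect size or power, so every rate below is an assumption that shows direction and rough size.

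**Inputs (assumed).** Hit rate H = 0.80; false-alarm rate F = 0.30, taken as a share of distracters.

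**Formulas.** d' = z(H) − z(F); criterion c = −0.5 × [z(H) + z(F)], where a higher c means less readiness to respond.

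**Baseline.** z(0.80) = 0.842 and z(0.30) = −0.524. So d' = 0.842 + 0.524 = 1.37 and c = −0.5 × (0.842 − 0.524) = −0.16.

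**Case 1: a uniform shift s towards not responding.** F becomes Φ(−0.524 − s), H becomes Φ(0.842 − s), and d' is unchanged by construction.
- s = 0.1: F = Φ(−0.624) = 26.6%, H = Φ(0.742) = 77.1%.
- s = 0.3: F = Φ(−0.824) = 20.5%, H = Φ(0.542) = 70.6%, and c = −0.16 + 0.30 = 0.14.

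At s = 0.3 the named variable improves by 30 − 20.5 = 9.5 points, while discrimination has not changed.

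**Case 2: random loss of 20% of all responses.** F = 0.8 × 30% = 24% and H = 0.8 × 80% = 64%. Then d' = z(0.64) − z(0.24) = 0.358 + 0.706 = 1.06. The named variable improves by 6 points while discrimination gets worse.

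**Range.** With hit rates of 0.70 to 0.90 and false-alarm rates of 0.20 to 0.40, losing 20% of responses always cuts the false-alarm rate by one fifth. d' always falls: the smallest starting value goes from 0.78 to 0.62 and the largest from 2.12 to 1.58.

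**Would reading hits beside false alarms expose this?** On the odds scale:
- Case 1, s = 0.3. False alarms: odds 0.30/0.70 = 0.429 become 0.205/0.795 = 0.258, ratio 0.60. Hits: 0.80/0.20 = 4.00 become 0.706/0.294 = 2.40, ratio 0.60. The falls match.
- Case 2. False alarms: 0.429 becomes 0.24/0.76 = 0.316, ratio 0.74. Hits: 4.00 becomes 0.64/0.36 = 1.78, ratio 0.44. Hits fall more.

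A joint reading supports a claim of selective inhibition in neither case. The named variable alone shows a gain in both.

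**The denominator matters.** If the percentage were false alarms relative to hits, Case 2 would cancel (30/80 = 0.375; 24/64 = 0.375). Case 1 would not (0.375 against 20.5/70.6 = 0.290). The text does not support that reading, but it does not state the denominator either.

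**The case against.** **Naming a primary variable does not exclude others.** This is right. The protocol scores hits and does not forbid their use. The SAP supplied is headed by primary hypothesis testing and refers to a section that is not in the documents. A reader might infer that hits will be ignored; the documents do not say so. What stands is that no companion measure and no rule for interpreting the two together is prespecified.

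**Drug-induced suppression is not documented.** Also right. A reader might infer that the active arms are expected to respond less, but no section says this. The Progressive Ratio task and the Stroop reaction times, collected in the same weeks, could reveal disengagement or slowing. However, nothing in the plan ties those results to the reading of the CPT.

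**Discrimination is a different construct.** A drug that helps people hold back may act partly through the criterion, and d' removes exactly that component. In Case 1 d' is null by construction, whether the cause is sedation or real restraint. The case for replacing the primary variable with d' is therefore not made. This stands, and d' belongs in a supporting role.

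**Pooling of distracter types.** The protocol says "Distracter stimuli consist of five-digit numbers that are completely different from the first, and numbers in which four of the five digits match the original", and its scoring rule does not separate the two. A reader might infer that pooling causes the suppression problem or dilutes a true effect. Neither is shown. A near-match false-alarm rate taken without hits would mislead in the same way. As for dilution, suppose near-matches are 25% to 50% of distracters and the others draw a constant 2% of responses. A 6-point fall on near-matches then shows as 0.25 × 6 = 1.5 to 0.50 × 6 = 3 points, but the SD shrinks by the same factor and the standardised effect does not change. The distracter mix is not given, and pooling itself is inferred from the scoring rule.

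**Conclusion.** The concern holds in a limited form. As written, the CPT outcome cannot separate better inhibition from less responding, although the score needed to separate them is already collected. On the assumed rates, a moderate general shift produces an apparent gain of about 6 to 10 points with discrimination unchanged or worse. The direction holds across the range tried; the size depends on the assumptions.

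The reach is narrow. The CPT is one of several laboratory tasks serving the mechanism hypothesis. A reader might infer that the efficacy result is at risk. It is not: cocaine use and retention are measured separately. What is at stake is whether a fall in false alarms may be called improved inhibition, or used as a mediator under that name. The change is worth making before data are analysed, because deciding afterwards how much weight hits deserve would be open to choice.

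**What to change.** In Protocol 7.2.2, with a matching paragraph in the SAP:

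1. Keep the percentage of false alarms as the primary CPT variable and state its denominator.
2. Prespecify the hit rate as a companion outcome in the same model. The generalized linear mixed model already planned for longitudinal data can take both, with item type (target or distracter) interacting with treatment and time.
3. Report d' and criterion as supporting indices.
4. Claim improved inhibition, or use the CPT as a mediator of inhibition, only if false alarms fall without a matching fall in hits. Define beforehand what counts as matching, for example through the item-type-by-treatment contrast.
5. Where the task software records distracter type, tabulate near-match and completely different distracters separately, as description.

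Hits are already scored, so items 1 to 4 need no new data. Item 5 depends on the software, because the protocol does not say that distracter type is stored. The cost is a short paragraph in each document, a little more analysis, and a slightly stricter condition for claiming improved inhibition. Raw false-alarm rates remain available for comparison with other work.

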7.2.3 IN TREATMENT

During the 9-week treatment phase participants will be scheduled to attend three clinic visits per week (MWF). Activities conducted at these visits will include urine testing, administration of study medication, cognitive behavioral therapy, and prize-based CM for attendance. Brief (5-10 min) evaluations by the study nurse will be conducted weekly to address concerns related to side effects, concomitant medications, and general adherence to the medication regimen.

7.2.4 COMPENSATION SCHEDULE

Participants will receive \$50 for completing the intake assessment phase of this study. Weekly assessments during treatment will take approximately 20 minutes to complete. Participants will earn prize bowl draws each time they attend a clinic visit (MWF) and provide a usable urine specimen. The prize-based CM is explained above (see Sect. 6.5). Behavioral tasks at Weeks -1, 3, 5, 7, and 9 will take approximately 65 minutes to complete. Participants will receive an additional \$25 (gift card) for each of these assessments, plus any task-specific earnings (approx. \$8). Subjects will also receive \$5 for each medication pack returned and bus/parking tokens as needed.

